## 10.15 Response Criteria for Patients with Lymphoma

The lymphoma response criteria are derived from the International Working Group consensus response evaluation criteria in lymphoma (RECIL 2017) (Younes, 2017).

#### **10.15.1** Assessment of Tumour Burden

Assessment of tumor burden in lymphoma should use the sum of longest diameters (SLD) of a maximum of three (3) target lesions in patients with disseminated disease (Younes, 2017). Target lesions should be selected from those with the largest size that can be reproducibly measured and preferably representing multiple sites and/organs. In most cases, lymph nodes can be considered target lesions if the lymph node longest diameter measures 15 mm or greater. Between ten (10) and 14mm is considered abnormal and should not be selected as target lesions and those less than ten (10) mm are considered normal (Schwartz 2009; Eisenhaur, 2009). Certain anatomical sites (such as, the inguinal, axillary, and portocaval), contain normal lymph nodes that may exist in a narrow, elongated form, and such nodes should not be selected as target lesions if alternatives are available. Extra-nodal lesions are selected as target lesions, if they have a soft tissue component, make the size threshold and have easy reproducibility for repeat measurements. All other lesions should be identified as non-target lesions, recorded at baseline (without measurements) and reported as either present, absent, or clear progression.

#### **10.15.2** Imaging and Baseline Scans

Whenever possible, the same imaging modality should be used at baseline and subsequently. CT scan imaging (with oral and intravenous contrasts) remains the gold standard for determining tumor measurements. In certain situations, where minimizing exposure to ionizing radiation is desirable, or where CT provides suboptimal assessment (such as primary bone lymphoma), standard MRI can be used to determine baseline and subsequent tumor measurements. [18F]2-fluoro-2-deoxy-D-glucose positron emission tomography (FDG-PET) is recommended in the initial staging work up all FDG-PET avid lymphomas (Cheson, 2014; Barrington, 2014). In certain cases, measurements may be performed on the CT-component of a combined PET/CT images, provided it has adequate resolution. Patients with diffuse large B-cell lymphoma with a

negative FDG-PET uptake in the BM (BM), do not rule out BM involvement, especially discordant histology; however, a positive FDG-PET uptake in the BM may obviate the need for a BM biopsy (Adams, 2014).

In patients with newly diagnosed lymphoma, a BM biopsy is recommended at baseline to determine the stage of disease and is mandatory for previously untreated patients with indolent B-cell lymphoma, mantle cell lymphoma, and T-cell lymphoma at the discretion of the local treating physician. Patients with Hodgkin lymphoma without FDG uptake in the BM or presence of B-symptoms do not need a BM biopsy at baseline, as BM in this situation is extremely unlikely to modify stage. Additional BM biopsies should be performed as part of usual clinical practice at the discretion of the local physician (Younes, 2017).

## **10.15.3** Response Assessment of Lymphoma

See the *Table 13* for the schedule of tumour evaluations. Response and progression of lymphomas will be evaluated in this study using the International Working Group consensus response evaluation criteria in lymphoma (RECIL 2017; Younes, 2017).

Table 13. RECIL 2017: Response categories based on assessment of target lesions (Younes,

**2017).** Percent change in the sum of diameters of target lesions from nadir.

	% change in SLD of Target Lesions from Baseline	FDG-PET	BM Involvement	New Lesions
Complete Response (CR)	
 
Complete disappearance of all target lesions and all nodes with long axis <10 mm;
 
≥30% decrease in the sum of the longest diameters of target lesions (PR) with normalization of FDG-PET.
 
	Normalization of FDG-PET (Deauville score 1-3).	Not involved	No
Partial Response (PR)	• ≥30% decrease in the sum of the longest diameters of target lesions but not a CR.	• Positive (Deauville score 4-5).	Any	No
Minor Response (MR)	• ≥10% decrease in the sum of the longest diameters of	Any	Any	No

	target lesions but not a PR (<30%).			
Stable Disease (SD)	• <10% decrease or ≤20% increase in the sum of the longest diameters of target lesions.	Any	Any	No
Progression of Disease (PD)	
 
>20% increase in the sum of the longest diameters of target lesions;
 
For small lymph nodes measuring <15 mm post therapy, a minimum absolute increase of 5 mm and the long diameter should exceed 15 mm;
 
Appearance of a new lesion.
 
	Any	Any	Yes or No

This revised definition of PD will eliminate the false interpretation of disease progression due to treatment-related inflammatory flares/ pseudo-progression reported with ICIs. The previous Lugano Criteria definition of PD is in conflict with clinical practice as it calls for stopping or changing therapy when a single lymph node increases in size from 1.0 to 1.6 cm, even though the overall sum of products may have shown significant reduction. (Witzig, 2009; Chanan-Khan, 2011). An increase in the size of previously involved small lymph nodes by >20% while other lesions are decreasing may be a pseudo-progression (especially at the beginning of treatment) and should not be designated a PD, unless there is continued increase in size on subsequent imaging studies (Witzig, 2009; Park, 2010; Armand, 2016, Zinzani, 2015, Younes, 2016). Patients should be allowed to remain on trial until the response or lack thereof is clarified on subsequent appropriate imaging, upon discussion with the investigators and patient and the Study Chair or Co-Chair. Confirmation of PD requires two consecutive scans at least four (4) weeks apart, and inclusion of new lesion measurements to the total tumor burden (Cheson, 2016; Younes, 2017).

Any mixed response will be called an MR, as long as the SLD is consistent with the aforementioned definition; however, MR will be called SD as long they fulfill all the criteria for SD in *Table 13*. Whenever possible, questionable small FDG-PET avid lesions should be confirmed by a histologic or cytologic analysis. Appearance of a new FDG-PET avid lesion that is smaller than the thresholds mentioned in *Table 13* should be closely monitored, and whenever possible, a biopsy should be performed to determine its nature.

To clarify, patients who achieve a CR (normalization of all lymph node measurements and disappearance of extra-nodal lesions), at least one previously involved lymph node should increase in size to measure 15mm in the long diameter, with a minimum absolute increase of at least 5mm from nadir to be considered for PD. Accordingly, an increase in a lymph node longest diameter from 8 to 13mm is not considered a PD, even though there is 38% increase in the measurement, since the lesion did not exceed 15 mm. Similarly, a change from 12 to 16mm does not qualify as a PD even though the new measurement exceeds 15 mm, since the absolute increase was <5 mm.

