	response criteria for solid tumours (revised for neuroblastoma using the				
	revised INRC), iRANO response criteria for CNS malignancies, RECIL				
	2017 response criteria for lymphomas, revised criteria according to				
	Creutzig, et al. (2012) for acute myeloid leukemia (AML; see Section				
	10.13), and response criteria as specified in Section 10.14 for acute				
Criteria for	lymphoblastic leukemia (ALL).				
Efficacy	Patients with response of 'stable disease' (SD) will also be reported as part				
Evaluation:	of the final analysis of clinical benefit, but will not contribute to the				
	primary efficacy outcome measure.				
	Secondary efficacy outcome measures:				
	PFS is defined as the time from the first dose of the study drug				
	administration to the occurrence of disease progression or death from any cause during the study.				
	OS is defined as time from first dose of study drug to death from any				
	cause.				
	A safety evaluation by the Safety Committee will be performed after				
Criteria for	Patient 1-Cycle 1, Patient 4-Cycle 1, Patient 7-Cycle 1, and Patient 10-				
Safety	Cycle 1. Enrollment will be held after each time point until a safety				
Evaluation:	evaluation of adverse events (AE) and serious adverse events (SAE)				
	confirms it is safe to resume enrollment.				
	confirms it is safe to resume enrollment.				

Toxicities will be described and defined in paediatric patients, focusing on SAEs, using the National Cancer Institute Common Terminology Criteria for Adverse Events (NCI CTCAE), version 4.03. Toxicities (drug-related AEs) of any grade, plus all Grade  $\geq$  3 AEs, all Grade  $\geq$  3 laboratory toxicities and all SAEs as defined in *Section 12* will be collected for this study.

The initial aim for this pilot study was to accrue 20 paediatric patients with biallelic mismatch repair disease (bMMRD) tumours. Following amendment, the study inclusion criteria are expanded to include those with hypermutant tumours (as determined by estimation of TMB by targeted next-generation gene sequencing), as well as patients with CMMRD tumours. Consequently, the total enrollment will be increased to 50 patients.

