# **10.15.5** Appearance of a New Extra-nodal Lesion

With the use of PET imaging, a new small PET avid lesion may appear during or after therapy. A minimum of 1 cm in largest diameter of new extra-nodal lesions is required to assign PD directly. New smaller but suspicious lesion should be designated as equivocal, and if later confirmed (by CT or biopsy) as being due to lymphoma, the documented date of progression should be the date of when it was first identified as equivocal.

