## **10.15.8** Integrating Target and Non-Target Lesions

In case of disseminated disease, the status of non-target lesions should be taken into account before formulating the final response status, as outline in *Table 15*.

*Table 15.* Response designation incorporating bet response of target lesions and non-target lesions (Younes, 2017).

lesions (Touries, 20			
Target Lesion	Non-target Lesion	New Lesion	Response Designation
CR	CR	No	CR
CR	PR,MR, or SD	No	PR (by CT with
			normalization of
			FDG-PET is CR)
CR	UE	No	UE
PR	UE	No	UE
PR	CR	No	PR
PR	PR,MR, or SD	No	PR
MR	UE	No	UE
MR	CR	No	MR
MR	PR,MR, or SD	No	MR
SD	UE	No	UE
SD	CR, PR, or MR	No	SD
SD	SD	No	SD
PD	Any	Yes/No	PD
Any	PD	Yes/No	PD
Any	Any	Yes	PD
CR	No	No	CR
PR	No	No	PR
MR	No	No	MR
SD	No	No	SD

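### For lymphoma, Table 13, Table 15 and 10.15.5 make a new lesion progression on first appearance, but the text of 10.15.3 requires a second scan at least four weeks later with the lesion added to the burden

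*Protocol*

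**What the plan says.** Four places in Section 10.15 of the Protocol bear on a new lesion in a lymphoma patient.

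- **Table 13 (in 10.15.3), PD row.** It lists more than a "20% increase in the sum of the longest diameters of target lesions" and, as a separate item, "Appearance of a new lesion". The row mentions no repeat scan and no size limit for a new lesion. Its only millimetre limits concern small nodes already being followed.
- **Table 15 (in 10.15.8).** It is captioned "Response designation incorporating bet response of target lesions and non-target" lesions. Whenever a new lesion is present the designation is PD, whatever the target and non-target status.
- **10.15.5.** "A minimum of 1 cm in largest diameter of new extra-nodal lesions is required to assign PD directly". A smaller suspicious lesion is equivocal and, if later confirmed, progression is dated to when it was first identified.
- **Text of 10.15.3, after Table 13.** It gives the purpose: "This revised definition of PD will eliminate the false interpretation of disease progression due to treatment-related inflammatory flares/ pseudo-progression reported with ICIs". It then says: "Patients should be allowed to remain on trial until the response or lack thereof is clarified on subsequent appropriate imaging", and closes with: "Confirmation of PD requires two consecutive scans at least four (4) weeks apart, and inclusion of new lesion measurements to the total tumor burden".

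The endpoints that use these rules are in the synopsis. ORR is CR plus PR, by RECIL 2017 for lymphoma. PFS runs from first dose of study drug "administration to the occurrence of disease progression or death from any cause during the study".

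**The concern.** A new lesion cannot be progression as soon as it is seen and also need a second scan, with its measurement added to the total burden, before progression is confirmed. No sentence in Section 10.15 ranks these statements.

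Progression status feeds PFS directly and best response indirectly. The patient affected is the one the 10.15.3 text sets out to protect: a lymphoma patient whose new lesion is a flare and then regresses. Two assessors who each follow the Protocol could record that patient differently.

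Other disease sections settle the matter. The iRECIST text separates unconfirmed from confirmed progression and resets the status if progression is not confirmed. The iRANO text back-dates confirmed progression to the first scan. The lymphoma section has a dating rule only for the small equivocal lesion, and it does not say whether a response after a first-scan PD counts.

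**Working it through.** The plan states no figure on this point, so there is none to reproduce. The check sets the rules side by side and runs an invented patient through each. The lesion sizes are assumptions.

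**Step 1. The rules compared**

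| Place | Second scan needed? | Size limit for a new lesion | New lesion added to the burden? |
|---|---|---|---|
| Table 13, PD row | Not stated | None | Not stated |
| Table 15, new-lesion row | Not stated | None | Not stated |
| 10.15.5 | No, if extra-nodal and at least 1 cm | 1 cm, extra-nodal only | Not stated |
| 10.15.3 text | Yes, at least 4 weeks apart | Refers to Table 13, which has none | Yes |

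**Step 2. One patient, both readings**

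Inputs: baseline target sum 60 mm. Scan 1: targets 50 mm plus a new 12 mm extra-nodal lesion. Scan 2, at least 4 weeks later: targets 38 mm, new lesion gone. Percentage change = sum / baseline - 1.

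- *Scan 1, Tables 13 and 15 and 10.15.5.* A new lesion is present and 12 mm exceeds 1 cm, so PD is assigned. It is a PFS event at scan 1.
- *Scan 1, 10.15.3 text.* Burden = 50 + 12 = 62 mm. Change = 62 / 60 - 1 = +3.3%, well short of a rise above 20%. Progression is not confirmed and the patient stays on trial.
- *Scan 2, 10.15.3 text.* Change = 38 / 60 - 1 = -36.7%, with no new lesion. This meets the 30% decrease for PR in Table 13. The patient is progression-free and can count in the ORR.
- *Scan 2, tables and 10.15.5.* The PFS event at scan 1 stands. The lymphoma section does not say whether the later response counts.

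The new lesion must resolve for this to reach the ORR. Table 13 requires no new lesions for CR, PR, MR and SD alike, so while the lesion persists the patient is not a responder on any page, however much the targets shrink.

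**Step 3. The size limit**

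Take a new 8 mm extra-nodal lesion. Read literally, Tables 13 and 15 give PD. Section 10.15.5 calls it equivocal. The 10.15.3 text says a new FDG-avid lesion below the Table 13 thresholds should be monitored closely and biopsied where possible, but Table 13 holds no threshold for a new lesion.

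**The case against.** The best defence is that the tables list what each category looks like at one time point, and the text straight after Table 13 says how PD is then confirmed. Neither table says that one scan suffices.

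For the criterion of a rise above 20% in the target sum, this defence stands: the row and the text can be read together. A reader might infer that the whole PD row contradicts the text, but the documents do not support that. The defence fails for new lesions. Section 10.15.5 assigns PD directly, which leaves no room for a confirming scan, and Table 15 states the resulting designation rather than an interim finding.

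A second defence is that the confirmation sentence closes a paragraph about flares in small nodes. The earlier sentences do concern those, but the confirmation sentence is worded for PD in general and names new lesions.

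A third is that the specific paragraphs refine the one-line table entry on size. This partly stands: most readers would probably apply the 1 cm limit of 10.15.5 to an extra-nodal lesion. The tables still do not carry it, and the cross-reference in 10.15.3 points to a threshold that is not there. The size gap is the lesser part of the point.

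**Conclusion.** The contradiction on new lesions is real and lies in the current text. A lymphoma patient with a new extra-nodal lesion of at least 1 cm that is not confirmed as progression, and that later resolves with target shrinkage of at least 30%, is a PFS event under Tables 13 and 15 and 10.15.5. Under the 10.15.3 text the same patient can be progression-free and a PR.

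The effect is limited to lymphoma patients who follow that course. The Protocol gives no expected number of lymphoma patients and no flare rate, so the effect on ORR or PFS cannot be calculated.

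Three stronger readings are tempting but not supported:

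- *The tables take the patient off therapy.* Neither table mentions stopping. Sections 3.2 and 5.1 discontinue for confirmed progression, 10.15.3 keeps the patient on trial meanwhile, and 13.2 lists progression as a withdrawal criterion only beyond 12 weeks after the start.
- *The PFS date always moves by at least four weeks.* No lymphoma text dates confirmed PD to the second scan, and the one lymphoma dating rule, in 10.15.5, back-dates. The clear PFS difference arises where PD is never confirmed.
- *The chance that a cohort lands exactly on its Simon boundary measures the impact.* It shows only that a go/no-go decision can turn on one response (for example 4 versus 5 of 20, or 5 versus 6 of 30). It does not give the chance that a reclassified lymphoma patient supplies that response.

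**What to change.** Reconcile Table 13, Table 15, 10.15.3 and 10.15.5 into one lymphoma rule that states:

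1. whether a new lesion needs confirmation before it counts as PD;
2. what size limit applies, for nodal and extra-nodal lesions, with the same limit in both tables;
3. whether the new lesion is added to the total burden;
4. which scan dates PD for PFS;
5. whether a response after an unconfirmed first-scan PD counts in the ORR.

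Confirmed progression also governs stopping treatment, so the choice of rule is for the sponsor. The passages must agree, whichever rule is chosen.

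The cost is wording in two tables and two paragraphs. If the sponsor keeps confirmation, no scan is needed beyond the second one that 10.15.3 already requires.

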## **10.15.4** Small Responsive Lymph Nodes

In cases where baseline tumor burden is low, and only a few lesions measuring around two (2) cm in longest diameter, treatment effect may shrink the long axis of a target lymph node to a normal value of <10 mm. Although the lymph node is now within normal size range (consistent with CR), the percentage of diameter reduction may be <30% (less than a PR). In these cases, a "normalized" diameter of "0, or resolved" should be used to calculate the SLD, to ensure accurate response designation (see sample calculation in *Table 14*).

**Table 14.** Sample calculating sum of diameters to include small responsive lymph nodes using normalized diameters (Younes, 2017).

Target Lesions	Lesion 1	Lesion 2	Lesion 3	SOD	% change from baseline	Response designation
Baseline (cm)	1.6	1.7	2.0	5.3	N/A	N/A
Nadir actual (cm)	0.9	1.4	1.8	4.1	23	MR
Nadir normalized (cm)	0; resolved	1.4	1.8	3.2	40	PR (or CR if PET -ve)

# **10.15.5** Appearance of a New Extra-nodal Lesion

With the use of PET imaging, a new small PET avid lesion may appear during or after therapy. A minimum of 1 cm in largest diameter of new extra-nodal lesions is required to assign PD directly. New smaller but suspicious lesion should be designated as equivocal, and if later confirmed (by CT or biopsy) as being due to lymphoma, the documented date of progression should be the date of when it was first identified as equivocal.

## **10.15.6** Measurement of Splitting Lesions

Frequently, effective therapy may convert a large confluent mass to several smaller constituent lymph nodes. In this case, the measurement of each lymph node should be carried out and entered in the calculation of sum of diameters. However, to avoid an overall increase in the number of target lesions, sub-designations of A, B, C, etc. for any target lesion that has undergone splitting should be created.

## **10.15.7** Spleen Measurement

The spleen vertical length can be calculated by multiplying the number of spleen slices in transverse CT views by the thickness of each slice, or by measuring splenic coronal diameter on a PET maximum intensity projection image.

## **10.15.8** Integrating Target and Non-Target Lesions

In case of disseminated disease, the status of non-target lesions should be taken into account before formulating the final response status, as outline in *Table 15*.

*Table 15.* Response designation incorporating bet response of target lesions and non-target lesions (Younes, 2017).

lesions (Touries, 20			
Target Lesion	Non-target Lesion	New Lesion	Response Designation
CR	CR	No	CR
CR	PR,MR, or SD	No	PR (by CT with
			normalization of
			FDG-PET is CR)
CR	UE	No	UE
PR	UE	No	UE
PR	CR	No	PR
PR	PR,MR, or SD	No	PR
MR	UE	No	UE
MR	CR	No	MR
MR	PR,MR, or SD	No	MR
SD	UE	No	UE
SD	CR, PR, or MR	No	SD
SD	SD	No	SD
PD	Any	Yes/No	PD
Any	PD	Yes/No	PD
Any	Any	Yes	PD
CR	No	No	CR
PR	No	No	PR
MR	No	No	MR
SD	No	No	SD

# 10.16 Response Criteria for Patients with More than One Tumour

In the rare event that a patient has more than one tumour (e.g. glioblastoma and colon cancer), the evaluation will take into account the combination of responses as follows: response = either of CR + CR, CR + PR, CR + SD, PR + SD, while the absence of response or progression will include all other situations.

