## 4.2.2 Part II - Treatment and Companion Biomarker Inclusion Criteria

In order to participate in **Part II**, patients must meet the following criteria:

- **1. Consent/ Assent:** Patient and Legally Acceptable Representative (LAR; such as a parent or guardian, as applicable) must be willing and able to provide written informed consent/assent for the trial as per local requirements.
- **2. Confirmation of Hypermutation or Proof of RRD:** patient must have completed and verified a sufficient TMB level or have proof of RRD diagnosed in the appropriate lab, as outlined in the *Lab Manual*.
- 3. Age: patients must be ≥ 12 months and < 25 years of age at the time of Part II enrollment.

  Local centres are only obligated to treat/ admit patients in accordance their age range capabilities.
- **4. Diagnosis:** patients must have had histologic verification of malignancy at the time of initial diagnosis or at relapse (as specified above). Patients with multiple concurrent and/or sequential neoplasms are eligible, including CNS and haematological malignancies.
- **5. Disease status:** patients must have either measurable or evaluable disease in accordance with criteria as outlined in *Section 10*. Tumour lesions situated in a previously irradiated area are considered measurable if progression has been demonstrated in such lesions.
- **6. Treatment options:** patient's current disease state must be one for which there is no known curative therapy or therapy proven to prolong survival with an acceptable quality of life. Chemotherapy-naïve patients will be eligible in cases where first-line therapy does not include chemotherapy (e.g. surgery alone for management of ependymoma).
- 7. Performance status: Karnofsky  $\geq 50\%$  for patients > 16 years of age or Lansky  $\geq 50$  for patients  $\leq 16$  years of age. Patients who are unable to walk because of paralysis, but who are

up in a wheelchair, will be considered ambulatory for the purpose of assessing the performance score.

- **8. Previous treatment:** patients must have fully recovered from the acute toxic effects of all prior anti-cancer therapy.
  - **a. Myelosuppressive chemotherapy:** at least 21 days after the last dose of myelosuppressive chemotherapy (42 days if prior nitrosourea).

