If iUPD is not confirmed at the next assessment, then the appropriate response will be assigned (iUPD if the criteria are still met, but no worsening, or iSD, iPR or iCR if those criteria are met compared to baseline). The prior documentation of iUPD does not preclude assigning iCR, iPR, or iSD in subsequent time-point assessments or as best overall response (BOR) providing that iCPD is not documented at the next assessment after iUPD. Tumour disease evaluation will be by objective response rate (ORR = complete response [CR] and partial response [PR]). Patients with response of 'stable disease' (SD), iCR, iPR, or iSD will also be reported as part of the final analysis of clinical benefit, but will not contribute to the primary efficacy outcome measure (Seymour, 2017).

Treatment beyond initial iUPD is permitted in patients who are clinically stable to continue on treatment until the next assessment (≥four [4] weeks later); this next imaging assessment should

be no longer than eight (8) weeks later, to ensure that patients remain fit for salvage therapies All decisions regarding continuation or discontinuation of therapy should be made by the patient, the local PI and either the Study Chair or Co-Chair. An assignment of clinical stability requires that no worsening of performance status has occurred, that no clinically relevant increases in disease-related symptoms such as pain or dyspnoea occur that are thought to be associated with disease progression, and that no requirement for intensified management of disease-related symptoms exists, including increased analgesia, radiotherapy, or other palliative care.

Patients who have iUPD and are not clinically stable should be designated as not clinically stable in the case report form. This designation will allow the best overall response to be calculated and the date of iUPD to be used in estimates of PFS.

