#### 11. STATISTICAL CONSIDERATIONS

This is a pilot study for which the initial aim was to accrue 20 paediatric patients with bMMRD tumours. Following amendment, the study inclusion criteria will be expanded to include those with hypermutant tumours (as determined by estimation of TMB by targeted gene sequencing), as well as those with CMMRD, including bMMRD tumours, and consequently the total enrollment will be increased to 50 patients.

The primary objective is to determine the ORR as well as to estimate the efficacy of nivolumab in patients with hypermutant tumours. The study is predicated on the hypothesis that patients with hypermutated tumours will derive greater benefit from nivolumab than those without; however, the relevant threshold of TMB is not yet established. Consequently, in this pilot study, patients will be recruited into two cohorts depending on TMB. This will provide the opportunity to treat patients with a relatively low TMB ( $\geq$ 5 to <10/Mb, estimated ~15% of tumors) to assess for responses to nivolumab, while a separate cohort for patients with TMB ( $\geq$ 10/Mb, estimated ~5% of tumors) will ensure that overall study enrollment is not dominated by patients with lower TMB.

A Simon two-stage design will be used within each cohort.

For cohort A (TMB ( $\geq$ 5 to <10/Mb), the null hypothesis that the true response rate is only 10% will be tested against a one-sided alternative. In the first stage, 10 patients will be accrued. If there are 1 or fewer responses in these 10 patients, the cohort will be closed. Otherwise, 10 additional patients will be accrued for a total of 20. The null hypothesis will be rejected if 5 or more responses are observed in 20 patients. This design yields a type I error rate of 0.05 and power of 85% when the true response rate is 35%. Accrual to this cohort will stop if evidence accumulates that the efficacy is lower than the specified acceptable levels. If five or more ( $\geq$ 5) patients experience objective responses (CR+PR), then we will conclude that Nivolumab is sufficiently active in patients with TMB  $\geq$ 5 to <10/Mb to warrant recommendation for continued investigation.

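### The rule for patients with more than one tumour leaves out PR + PR, so partial response in both tumours is classed as non-response while PR + SD is a response

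*Protocol*

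**What the plan says.** Section 10.16 opens with "In the rare event that a patient has more than one tumour" and sets the rule: response means "either of CR + CR, CR + PR, CR + SD, PR + SD, while the absence of response or progression will include all other" situations.

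Such patients can enter the trial. The Part II inclusion criteria (Section 4.2.2, Diagnosis) state: "Patients with multiple concurrent and/or sequential neoplasms are eligible, including CNS and haematological malignancies".

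The primary endpoint is the objective response rate, which the synopsis and Section 10.2.7 define as CR and PR. Section 11 feeds the count of CR and PR into a two-stage rule in each cohort. Each cohort closes with 1 or fewer responses in its first 10 patients. For Cohort A, "The null hypothesis will be rejected if 5 or more responses are observed in 20 patients"; for Cohort B the bar is 6 of 30. Stated power is 85% at a true rate of 35% in Cohort A and 80% at a true rate of 30% in Cohort B.

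**The concern.** The list is closed and everything off it is sent to non-response or progression, so an assessor cannot read PR + PR into it. The classification then runs against the order of benefit: if the second tumour improves from SD to PR, the patient moves from responder to non-responder. No reason is given for treating the better result as a failure.

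The rule decides who counts in the primary endpoint. It also leaves an awkward choice if the case arises. Applied literally, it drops a patient whom the endpoint definition would count. Set aside after the result is known, in an open-label single-arm trial, it becomes a post hoc change to the primary endpoint.

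**Working it through.** **Classification.** With four categories per tumour (CR, PR, SD, PD) there are 10 unordered pairs. Applying Section 10.16 as written:

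- Response: CR+CR, CR+PR, CR+SD, PR+SD (4 of 10).
- Not response: PR+PR, SD+SD, CR+PD, PR+PD, SD+PD, PD+PD (6 of 10).

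Five of the six excluded pairs either contain a PD or contain no CR or PR. PR+PR is the only excluded pair that has a CR or PR and no PD.

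**Comparison with the rest of the protocol.** The endpoint counts PR as a response (synopsis, Sections 10.2.7 and 11). Where the protocol combines components within one disease, it treats PR with PR as PR: lymphoma Table 15 (target PR with non-target PR) and the neuroblastoma overall response in Section 10.7.1 (PR in all soft tissue and bone sites). No other section on patients with several tumours supplies the missing pair.

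**Power of the stated designs.** With 10 patients in stage 1, continuation at 2 or more responses, total n and final bar r:

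power(p) = Σ (x = 2 to 10) C(10,x) pˣ (1−p)¹⁰⁻ˣ × P[Bin(n−10, p) ≥ r−x]

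- Cohort A, n = 20, r = 5, p = 0.35: 84.3% (stated 85%).
- Cohort B, n = 30, r = 6, p = 0.30: 81.5% (stated 80%).

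Both are within 2 points of the stated power. Section 11 gives no null rate for Cohort B, but power does not need one.

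**Effect of losing responders.** If a share m of true responders is recorded as non-responders, the observable rate is p(1−m), and it applies at both stages. The protocol gives no value for m, so the values below are assumptions.

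| m (assumed) | A: 0.35(1−m) | A: power | B: 0.30(1−m) | B: power |
|---|---|---|---|---|
| 0 | 0.3500 | 84.3% | 0.300 | 81.5% |
| 1% | 0.3465 | 83.6% | 0.297 | 80.8% |
| 2% | 0.3430 | 82.9% | 0.294 | 80.0% |
| 5% | 0.3325 | 80.5% | 0.285 | 77.7% |

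The loss is about 0.7 points at 1%, about 1.5 points at 2% and just under 4 points at 5%, in either cohort. The error only removes responders: it lowers the observed rate and power and cannot inflate the type I error.

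**One patient.** A single PR+PR patient shifts the observed rate by 1/20 = 5 percentage points in Cohort A or 1/30 = 3.3 in Cohort B. That patient is decisive only if the count sits at an edge: 1 v 2 of 10, 4 v 5 of 20, or 5 v 6 of 30.

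**The case against.** The strongest reply is that this is an obvious drafting slip with little practical reach. CR+PR and PR+SD both count, the endpoint is CR plus PR, and responders' images go to central review (Section 8.3), so an assessor would probably count PR in both tumours. Section 10.16 itself calls the situation rare. Eligibility covers sequential as well as concurrent neoplasms, and a past, treated cancer need not give a second tumour to assess. Screening for concurrent malignancies is recommended, not required. A patient is lost only if two tumours are assessed and both reach PR. For illustration, if 5% of responders had two assessed tumours and 20% of those were PR+PR, m would be 0.05 × 0.20 = 1%.

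This stands as an argument about size. It does not repair the text, because the default clause is explicit and leaves nothing to infer.

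A reader might go further and infer a large loss of power by raising each final bar by one response. That gives 84.3% to 73.5% in Cohort A (6 of 20) and 81.5% to 75.9% in Cohort B (7 of 30). The arithmetic is right, but the documents do not support it as the expected effect. It assumes that one responder is certain to be lost in each cohort. At the design rates the expected responders are 0.35 × 20 = 7 and 0.30 × 30 = 9, so one loss is about 14% or 11% of them. It also leaves the stage 1 bar unchanged, although a loss among the first 10 patients would count there too. Nor does eligibility for multiple neoplasms show that the case is likely.

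**Conclusion.** The rule is wrong as written: it excludes PR+PR, puts it below PR+SD and contradicts the protocol's own endpoint. This follows from the text alone and rests on no assumption.

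The expected effect on the trial is small. On the assumed shares of 1% to 5% of responders lost, power falls by roughly 1 to 4 points in each cohort, and the lower part of that range fits better with a situation the protocol calls rare. The true share is unknown. The case for correction is that a primary-endpoint rule should be right before it is applied, and that decisions on counts this small can turn on one patient. A large or likely loss of power is not shown.

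**What to change.** Either add PR + PR to the list in Section 10.16, or restate the rule: response = at least one CR or PR and no PD in any tumour. Over CR, PR, SD and PD the general wording gives the current four pairs plus PR+PR (5 of 10), and it also covers more than two tumours. If it is chosen, one clause should say how a tumour that cannot be evaluated is handled, since CR or PR with a non-evaluable tumour is not a response under the present list but would meet the general wording.

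The cost is a one-line amendment. It changes endpoint classification only, not treatment, sample size or decision thresholds. It should be made before response data are analysed, so that no patient is reclassified with the result in view.
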